2.1 Background

Ultrasound has become a bedside tool and clinical skill widely used in internal medicine, primary care and other settings. Medical graduates first encounter it in early residency, so Swiss clinicians and programme directors agree that ultrasound training should become integrated into the undergraduate curriculum. Institutions are changing their curricula accordingly, often supplementing traditional teaching with 'near-peer' tutoring through classes held by advanced peers. Near-peer tutoring has been found to be both effective and cost-effective. Ultrasound education is lagging behind in Switzerland, where we have no consistent ultrasound training for medical students. The most popular course in postgraduate training is a resource-intensive 21-hour basic course for abdominal ultrasound. However, this is expensive, and may not be the best way to impart these skills to undergraduates, who need training more adapted to their needs. We therefore developed a 21-hour blended-learning ultrasound course, comprising 5 hours of e-learning and 16 hours of near-peer tutoring. Students and their nearpeer tutors autonomously organize individual practical teaching sessions within a 16 weeks period. Enrolment started in January 2019. We want to determine whether our curriculum is as good as, or better than, the existing 21-hour course. We also want to better understand how to achieve effective student-centred learning supported by near-peer tutoring.

2.2 Objectives

The aim is to compare a new 21-hour blended-learning ultrasound course (5 hours of e-learning and 16 hours of near-peer tutoring) with the standard 21-hour faculty-led basic ultrasound course.

3 Study methods

3.1 Trial design

The SIGNATURE trial will be a multicentre, open-label randomized controlled noninferiority trial with two parallel arms, Figure 1.

The students in one arm will have only the new blended learning course, whereas the other arm will have only the standard faculty-led course.

3.2 Randomization

We will use centralized computed randomization in blocks of 4 to allocate each of the participants to one of the two study arms, with allocation in a 1:1 ratio, stratified by study site. The reason for block randomisation is the requirement of the control group to comprise of exactly 24 or 28 students due to the max. group size of 4 students per tutor. The randomization will be performed by an external partner (CTU Bern). An independent statistician of CTU Bern, who is not otherwise involved in the trial, will receive a list of participants of each site that contains the participant ID but no identifying data and will randomly allocate entries to either treatment arm. The generated allocation sequence will be password-protected and sent back to the trial coordinator. This procedure will ensure concealment of

allocation, i.e. randomization will be done without the influence from investigators or study personnel.

Figure 1: Study methods summary

3.3 Sample size

Based on a pilot with 20 students we expect a mean score of 33 out of 50 points per station with a standard deviation (SD) of 4 points. The study was powered for noninferiority using a margin of -1.5 points for the difference in mean OSCE score between the intervention and control group in the practical exam at 6 months (primary outcome). A difference of 1.5 points would correspond to an effect size of 0.375 standard deviations (SD), which we would still consider as non-inferior. We calculated the sample size with the assumption that the intervention group will

perform somewhat better (+0.5 points in mean OSCE score) than the control group based on test

results from previous pilots. We chose a one-sided alpha-error of 0.05 and a power of 90% which yielded 138 participants (69 in each arm). Allowing for a 9% dropout rate we decided to include 152 students.

3.4 Framework

This is a non-inferiority trial. The working hypothesis is that students from the blended learning group will perform as good or better than the students that took part in a standard basic abdominal ultrasound course 6 months after finishing the course.

3.5 Statistical interim analysis No statistical interim analyses are planned.

3.6 Timing of outcome assessment

- Assessment of the outcomes will be as follows:
 - immediately after the course programmes:
 - OSCE scores;
 - 6 months after the end of the course programmes:
 - OSCE scores (primary outcome);
 - number of optional post-course training hours taken.

To adapt to local curriculum timetabling, the assessments for the three sites will not be performed at the same time.

3.7 Timing of final analysis

• After completion of the 6-month OSCEs at all three sites.

3.8 Blinding

OSCE assessors will be blinded to group allocation. The assessments will be at the same time for each group. Students will be instructed not to reveal their group allocation to the OSCE assessors.

4 Statistical principles

4.1 Confidence intervals and p-values

Non-inferiority will be assessed based on a one-sided 95%-confidence interval for the difference in the primary outcome, the mean OSCE score at 6 months, between the two groups. If the lower confidence limit lies above the non-inferiority margin of -1.5 points, we will claim non-inferiority.

If non-inferiority can be established, we will test for superiority of the blended learning group at a two-sided alpha level of 0.05. This stepwise testing approach will keep the overall family-wise type-I error rate at the nominal 5%-level. For secondary outcomes, a two-sided p-value of 0.05 will be considered statistically significant. Results will be reported with corresponding two-sided 95% confidence intervals. There will be no adjustments for multiple testing of secondary outcomes.

4.2 Adherence and protocol deviations

Participants will be considered adherent to the interventions when they have completed the allocated 21 hours of training.

Non-adherence and protocol deviations will be summarized as number and frequency.

4.3 Analysis population

4.3.1 Full analysis set (FAS)

The full analysis set (FAS) will include all randomized subjects. Following the intent-to-treat principle, subjects will be analyzed according to the intervention they are assigned to at randomization.

4.3.2 Per-protocol (PP)

The per-protocol population consists of all subjects in the FAS who do not have any protocol deviation that could confound the interpretation of analyses conducted on the FAS. The following are common major protocol deviations:

- More than 5 hours of previous formal ultrasound training
- Additional practical ultrasound training during the phase between randomisation and first OSCE (other than the training within the study)
- Not completing the assigned training
- Not attending both ultrasound exams

5 Trial population

5.1 Screening data

We will invite all students that belong to a certain study year at the respective university (typically 120-240). The year is selected with regards to best compatibility of the respective study year timetable at a given university with the study procedures. The invitation is sent out during a face-to-face short presentation following a regular lecture of the respective study year as well as through student forums and social media plattforms of the respective study year.

Based on the eligibility criteria, students that decide to take part in the study are expected be more motivated to learn ultrasound than non-participating students. There may also be some students that are not eligible because they are already too advanced in ultrasound skills.

We will not collect any data on non-participating candidates.

5.2 Eligibility

Students of human medicine at one of three Swiss universities (Bern, Freiburg, Zurich, in the 3rd to 8th semester) are eligible for study participation if they are:

- willing to participate in the study and give their consent to take part in the research;
- willing to pay the 200.- CHF course fees (partial reimbursement of tutors and administrative fee for the SGUM course certificate);
- fill out the baseline questionnaire.

Exclusion criteria for study participation are:

- Did not sign the study agreement or pay the course fee;
- More than 5 hours of previous formal ultrasound training;

• Failure to fill out baseline questionnaire.

5.3 Recruitment

We will primarily recruit students in semester 7 in Bern (total medical student intake per year = 220), in semester 6 in Zurich (240) and Fribourg (120). A CONSORT participant flow diagram will be drawn following the CONSORT 2010 standards (http://www.consort-statement.org/consort-2010).

5.4 Withdrawal and follow up

Participants who do not complete their allocated 21 hours of training will be considered not to have completed the intervention. They will still undergo both OSCEs and will be analyzed on an intention-to-treat-basis, but excluded from the per-protocol analysis.

Participants that did not complete the allocated training or did not attend the two ultrasound examinations (OSCE) will be shown in the CONSORT participant flow diagram.

5.5 Baseline characteristics

We will collect the following baseline characteristics:

- Demographics: age (numeric), gender (F/M), semester (numeric), university (categorical)
- Previous ultrasound experience: owning an ultrasound textbook (yes/no), hours of previous practical experience in ultrasound, hours of formal teaching in ultrasound.
- Preference for future specialisation (list of options plus 'other' option).

Baseline characteristics will be descriptively summarized showing number and proportion for categorical data and mean and standard deviation or median and interquartile range for continuous data. No p-values will be displayed because any significant difference can be explained by the play of chance if the randomization was performed properly.

Description	Variable	Туре
Age	age	Numeric/continuous: years
Gender	gender	Categorical/binary: Male, Female
Semester	Semester	Numeric/discrete, 1-12
Universtity	University	Categorical/nominal: Bern, Freiburg or Zürich
Formal ultrasound training	Formal training	Numeric/continuous, hours
Previous ultrasound experience	Experience	Numeric/continuous, hours (Watching, doing)

6 Analysis

6.1 Outcome definitions

6.1.1 Primary outcome

The primary outcome will be students' ultrasound skills measured by a six-station OSCE six months after the end of their courses (mean score).

To assess the outcome, an objective structured clinical examination (OSCE) has been adapted from the validated version of Hofer et al., 2012. Every station in the six-station OSCE has a maximum of 50 points.

6.1.2 Secondary outcomes

- students' OSCE scores immediately after their courses (mean score); see description above
- additional hours of self-training during the follow-up phase;

Table 2:	Derivation	of primar	v and sec	condary	outcomes.
	20111011011	0. p	,		

Outcome	eCRF sheet	Variable	Variable type	Derivation	Outcome type
Primary: OSCE score six months after course	Excel sheet output from electronic data entry (iPad)	Subscores at OSCE stations 1-12	Numeric	Sum of scores at individual stations (0-50 pts) divided by number of stations	Continuous
OSCE score immediately after course	Excel sheet output from electronic data entry (iPad)	Subscores at OSCE stations 1-12	Numeric	Sum of scores at individual stations (0-50 pts) divided by number of stations	Continuous
Additional hours of self-training	Online Survey before 2 nd OSCE (RedCap)	Survey questions asking on additional self-training	Numeric	Simple number between e.g. 0-100 hours	Continuous

6.2 Analysis methods

6.2.1 Primary analysis

As recommended by the CONSORT statement for non-inferiority trials, we will perform both intention-to-treat (ITT) and per-protocol (PP) analyses. For the primary outcome, ITT and PP analyses must reach the same conclusion to establish noninferiority. For secondary outcomes, the ITT analysis will be the primary analysis, the PP analysis a secondary analysis.

We will use a repeated-measures mixed-effects linear model with robust standard errogrs to compare the mean OSCE scores of both groups 6 months after the course (primary outcome) as well as immediately after the course (secondary outcome), taking into account the possible dependence of data within sites, participants, and series. The model will include the averaged OSCE score over all six stations of a series of each participant at both time points as dependent variable, fixed terms for the learning group, the type of series, the time point and the interaction term between learning group and time point, and random terms for site and participant. We will assess non-inferiority based on a one-sided 95% confidence interval for the difference in mean OSCE score between the two groups 6 months after the course. If the lower confidence limit lies above the non-inferiority margin of -1.5 points, we will claim non-inferiority. If non-inferiority can be established, we will test for superiority of the blended learning group at a two-sided alpha level of 0.05. This stepwise testing approach will keep the overall family-wise type-I error rate at the nominal 5%-level.

The difference in mean OSCE score immediately after the course will be assessed from the same model described above and presented with a two-sided 95% confidence interval and corresponding p-value.

The difference in median number of additional hours of self-training will be assessed from a quantile regression using robust standard errors to account for dependence of data within sites, and presented with a two-sided 95% confidence interval and corresponding p-value.

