6.5 Statistical software

Analyses will be performed with Stata version 16 or later (StataCorp, College Station, TX, USA).

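### On the reading consistent with the primary model, its robust standard errors rest on three site clusters, so the stated 5% error control does not hold; the SAP names no cluster level or degrees of freedom

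*SAP*

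**What the plan says.** SAP section 6.2.1 specifies a "repeated-measures mixed-effects linear model with robust standard errogrs to compare the mean OSCE scores of both groups 6 months after the course", described as "taking into account the possible dependence of data within sites, participants, and series". The fixed terms are learning group, series, time point and "the interaction term between learning group and time point, and random terms for site and participant". Section 5.2 restricts entry to "Students of human medicine at one of three Swiss universities", and section 3.2 describes randomisation in blocks of four, "with allocation in a 1:1 ratio, stratified by study site".

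Non-inferiority is claimed if the lower one-sided 95% limit for the 6-month difference exceeds -1.5 points, and the ITT and PP analyses must agree. Superiority of blended learning is then tested at a two-sided 5%. Sections 4.1 and 6.2.1 both state that this sequence holds the family-wise error at 5%.

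Neither section gives the cluster level of the robust variance, a small-sample correction or a reference distribution. Section 6.5 says "Analyses will be performed with Stata version 16 or later" but gives no command or option. For self-training hours, section 6.2.1 explicitly uses robust errors to handle dependence within sites. The fallback model in section 6.2.3 drops the participant term and keeps site.

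**The concern.** A sandwich variance is built from the score contributions of independent units and is reliable only when there are many of them. Once site is a random term, observations from the same site are correlated by assumption, so the only independent units in the written model are the three sites. A robust variance consistent with that model is a sum over three contributions, and nothing in the SAP directs the analyst elsewhere.

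The limit compared with -1.5 and the superiority p-value both come from this standard error. With three clusters it depends mainly on how closely three site-level differences happen to agree. Chance agreement gives a standard error that is far too small and can produce a false non-inferiority claim. Chance disagreement can lose a true one.

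**Working it through.** **Inputs from the SAP.** Three sites (5.2). Margin -1.5, SD 4, assumed true difference +0.5, one-sided alpha 0.05, power 90%, 138 participants, 152 with 9% dropout (3.3). Decision rule and the requirement that ITT and PP agree (6.2.1).

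**Assumptions, not in the SAP.** Site sizes, site variance, within-student correlation, series assignment, and the share of participants excluded from PP.

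**1. The plan's own figure.** n per arm = 2σ²(z₀.₉₅ + z₀.₉₀)² / (0.5 + 1.5)² = 2 × 16 × (1.645 + 1.282)² / 4 = 68.5, so 69 per arm and 138 in total. Then 138 / 0.91 = 151.6, so 152. The sample size reproduces. The implied standard error is 4√(2/69) = 0.681.

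**2. Error per test with three clusters.** Because randomisation is within site, the 6-month contrast is close to an average of three site-level differences. With the G/(G-1) factor, its site-clustered variance is close to their sample variance divided by three. The test statistic then behaves approximately as t on 2 df, for which P(T > c) = ½[1 − c/√(2 + c²)]. Without the factor, the standard error is multiplied by √(2/3) = 0.816, so c becomes 0.816c.

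| Test, normal critical value | With factor | Without factor | Nominal |
|---|---|---|---|
| Non-inferiority, c = 1.645 | 12.1% | 15.6% | 5% |
| Superiority in favour of blended learning, c = 1.96 | 9.5% | 12.5% | 2.5% |

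**3. Spread of the standard error.** With the factor it varies as 0.681 × √(χ²₂/2). The 5th percentile is 0.681 × √(0.103/2) = 0.15 and the 95th is 0.681 × √(5.991/2) = 1.18.

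**4. Simulation at a true difference of -1.5.** Each scenario had 3000 runs, using the mixed model's GLS estimator with variance components held at their true values. Sites were 48/48/56 or 24/48/80, dropout 0 or 9%, within-student correlation 0.5 or 0.7, and site variance 0, 0.5 or 2.

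| Variance and critical value | False non-inferiority, per test |
|---|---|
| Site sandwich with factor, normal | 11.4-13.0% |
| Site sandwich without factor, normal | 14.8-16.7% |
| Site sandwich with factor, t on 2 df (2.92) | 4.8-6.3% |
| Sandwich clustered on participant, normal | 5.1-6.1% |
| Model-based with site in the model, normal | 4.9-5.6% |

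Monte Carlo error at 12% is √(0.12 × 0.88/3000) = 0.6 percentage points, so the simulation agrees with step 2.

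**5. The joint ITT-and-PP rule.** This takes three equal sites, PP dropping 5%, 10% or 20% of participants at random, and the same true difference in both sets.

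| PP exclusions | With factor | Without factor | Valid SE |
|---|---|---|---|
| 5% | 9.9% | 13.1% | 4.1% |
| 10% | 9.0% | 12.1% | 3.7% |
| 20% | 7.7% | 10.6% | 3.2% |

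**6. A t(2) critical value as the remedy.** It brings the error back to about 5%, but power at a true difference of +0.5 falls from 90% to about 60%.

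**The case against.** The strongest reply is that the SAP never says the sandwich is clustered on site. That is correct. Site clustering is inferred from the model structure, and section 6.5 names a package without a command or option. If the analyst clustered on participant, each test would run near 5%. The problem is therefore conditional. But no section names participant as the cluster level, the wording on dependence lists sites first, and the self-training analysis uses robust errors for site dependence explicitly. A choice that moves the error per test from about 5% to 12-16% should not be left open for a primary confidence limit.

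Four stronger readings are tempting, and the documents do not support them:

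- *The trial's false non-inferiority rate is 12-16%.* That is the rate for one analysis. Section 6.2.1 requires ITT and PP to agree, which lowers the joint rate to about 8-13% under the assumed exclusions.
- *The superiority error is 19-25%.* That range counts rejections in both directions. The claim at issue is superiority of blended learning, so only the upper tail counts: 9.5-12.5% against 2.5%, before allowing for the requirement that non-inferiority be shown first.
- *The random site term is itself the fault.* With model-based standard errors, models that accounted for site in this way held about 5%. The cause is the sandwich summed over three clusters.
- *The sample size is wrong.* It reproduces exactly and is unaffected.

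It is also fair to say that the simulation held variance components at their true values and did not estimate them, and that its site sizes are assumed: section 3.2 mentions control groups of 24 or 28 without saying that this is per site. The t(2) calculation uses neither site sizes nor within-student correlation, and gives the same answer.

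**Conclusion.** The point stands as a conditional one. On the reading consistent with the written model, and with a normal critical value, the 5% control stated in sections 4.1 and 6.2.1 does not hold: about 12-16% per non-inferiority test, about 8-13% under the joint rule (against 3-4% with a valid standard error), and about 9.5-12.5% for a false superiority claim taken alone (against 2.5%). These figures rest on clustering at site, a normal reference distribution, the t(2) approximation, and, for the joint rule, PP exclusions of 5-20%. The fallback in section 6.2.3 offers no protection, since it keeps site as the grouping level. Because the primary decision depends on this limit, the variance estimator should be settled before analysis.

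**What to change.** Do not base the primary confidence limit on a site-clustered sandwich. In section 6.2.1, enter site, the stratification factor, as two fixed indicators and keep participant as the only random or cluster level. Then name one of:

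- model-based (REML) standard errors with a stated small-sample degrees-of-freedom method; or
- robust standard errors clustered on participant.

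Keeping the random site term with model-based standard errors is an acceptable alternative. In every case, state the type of standard error, any cluster level and the reference distribution. Carry the same choice into the fallback and sensitivity models of section 6.2.3 and the exploratory models of section 6.2.4.

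The cost is SAP wording and, with fixed site effects, 2 degrees of freedom. Data collection and sample size do not change.

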6.2.4 Additional analyses

We will explore the association of different factors such as gender, hours of additional training, motivation for ultrasound and mean group size with OSCE scores six months after the course using multivariable mixed-effects linear models with robust standard errors.

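### Faculty-led students are taught in groups of up to four per tutor, but neither the sample size nor any planned model allows for teaching-group clustering; if scores correlate within groups, the non-inferiority limit is too favourable

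*SAP*

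**What the plan says.** - **Design and teaching units.** Section 3.2 randomises students individually, 1:1, stratified by site. It explains the blocks by the need for a control group of 24 or 28, "due to the max. group size of 4 students per tutor". Section 2.1 describes the blended arm differently: students and near-peer tutors arrange their own practical sessions over 16 weeks, and no group size is given.
- **Sample size.** Section 3.3 plans "using a margin of -1.5 points for the difference in mean OSCE score", expects the intervention group to "perform somewhat better (+0.5 points in mean OSCE score) than the control group", and takes an SD of 4. It reports "a power of 90% which yielded 138 participants (69 in each arm"), raised to 152 for 9% dropout. No ICC or design effect appears.
- **Primary model.** Section 6.2.1 uses a repeated-measures mixed model with robust standard errors, "taking into account the possible dependence of data within sites, participants, and series". Its random terms are site and participant. The level at which the robust errors are clustered is not stated.
- **Other models.** Section 6.2.3 considers station, series, assessor and a random slope, but not tutor or teaching group. Group size enters only in 6.2.4, which explores the association of "motivation for ultrasound and mean group size with OSCE scores six months after the course".

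**The concern.** This is an individually randomised trial in which at least one arm is taught in groups. Students who share a tutor share the quality of that teaching, and it acts directly on the skill that the OSCE measures. Their scores may therefore be correlated within a group even though they were randomised one by one. A participant random effect handles the two measurements on one student, and a site effect handles differences between universities. Neither handles correlation between students of the same tutor within a site.

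If that correlation is positive and left out, the standard error of the difference is too small and the lower confidence limit too high. In this trial non-inferiority is claimed when that limit exceeds -1.5 points, so the error runs towards a false claim. The 90% power would also be optimistic for an analysis with a correct standard error.

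**Working it through.** **Inputs from SAP 3.3:** margin -1.5, assumed true difference +0.5, SD 4, one-sided alpha 0.05, power 90%, dropout 9%. **From 3.2:** at most four students per tutor in the control arm. **Assumed, because the SAP does not give them:** the ICC (0 to 0.10), and stable, non-overlapping groups of exactly four.

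**Step 1: reproduce the plan's figure.** The distance from the assumed difference to the margin is 0.5 + 1.5 = 2.0.

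n per arm = 2 × [4 × (1.645 + 1.282) / 2.0]² = 68.5, so 69 per arm and 138 in total. Then 138 / 0.91 = 151.6, so 152.

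The stated numbers reproduce exactly with a design effect of 1. At 69 per arm, SE = 4 × √(2/69) = 0.681 and power = Φ(2.0/0.681 − 1.645) = 90.2%.

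**Step 2: allow for teaching groups.** For a clustered arm, DE = 1 + (4 − 1) × ICC. The variance of the difference is multiplied by D, the mean of the two arms' DEs:
- control arm only clustered: D = 1 + 1.5 × ICC
- both arms clustered: D = 1 + 3 × ICC

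One-sided error of one analysis that ignores clustering = Φ(−1.645/√D).
Power with a correct SE at 69 per arm = Φ(2.0/(0.681 × √D) − 1.645).

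| ICC (assumed) | D, control only | Error | Power | D, both arms | Error | Power |
|---|---|---|---|---|---|---|
| 0 | 1.000 | 5.0% | 90.2% | 1.00 | 5.0% | 90.2% |
| 0.01 | 1.015 | 5.1% | 89.8% | 1.03 | 5.3% | 89.4% |
| 0.02 | 1.030 | 5.3% | 89.4% | 1.06 | 5.5% | 88.6% |
| 0.05 | 1.075 | 5.6% | 88.3% | 1.15 | 6.3% | 86.3% |
| 0.10 | 1.150 | 6.3% | 86.3% | 1.30 | 7.5% | 82.4% |

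Worked line, control only, ICC 0.05: √1.075 = 1.037. Error = Φ(−1.645/1.037) = Φ(−1.586) = 5.6%. Power = Φ(2.0/0.706 − 1.645) = Φ(1.188) = 88.3%.

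Groups below the maximum reduce the effect. With control-only groups of three at ICC 0.05, D = 1 + 0.5 × 2 × 0.05 = 1.05, which gives 5.4% error and 88.9% power.

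**Step 3: do the robust standard errors already cover this?** It depends on the unstated cluster level.
- Clustered on participant, they ignore teaching groups.
- Clustered on site, they cover groups nested in sites in principle, but there are only three sites. A simple simulation (three sites, six groups of four per arm and site, uncorrected site-level sandwich, normal limits) gave about 15% one-sided error even at ICC 0.
- Clustered on teaching group, the same simulation gave 5.2% at ICC 0 and 5.8% at ICC 0.10 with both arms clustered.

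**The case against.** **The ICC is unknown.** A reader might infer that the error rate is above 5% and power below 90% as a matter of fact. The SAP does not support that, because both statements need an ICC above zero and none is given. At ICC 0 nothing is lost, and at 0.01 the effect is negligible. This part of the objection stands, and the point is conditional on it.

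**The group structure is thinly documented.** A reader might also take both arms to be taught in fixed fours and quote 7.5% and 82.4%. Section 3.2 gives four as a maximum and only in connection with the control group. Sessions in the blended arm are self-organised, and the use of mean group size in 6.2.4 suggests that group size varies. Nothing in the SAP says that a student keeps one tutor in either arm, and such delivery detail may sit in the protocol. This also stands: the control-only column is the better supported one, and it too assumes stable groups.

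**The robust errors and the joint ITT/PP rule may protect.** The robust errors help only if clustered on teaching group, which 6.2.1 does not say. Requiring ITT and PP to agree cannot raise the false-claim rate and may lower it somewhat, so the table applies to a single analysis. But both analyses use the same model and the same kind of standard error, so the joint rule does not repair the omission.

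**A group variance is hard to estimate.** With about 17 groups of four in one arm (69/4), a simple between-group variance estimate would be zero or below about 45%, 35% and 21% of the time at ICC 0.02, 0.05 and 0.10. That is fair, and it argues against relying on the random intercept alone.

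**Conclusion.** The omission is real. The sample size assumes independent students, and no planned model has a term for tutor or teaching group, although the SAP considers series and assessor effects. The robust standard errors as written do not clearly cover it.

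The consequence is conditional and modest. In the better supported case, with fixed groups of four in the control arm only, an ICC of 0.02 to 0.10 adds 0.3 to 1.3 percentage points to a one-sided error of 5%. It takes 0.8 to 3.9 points off a power of 90.2% when the standard error is correct. If the blended arm were also in fixed fours, the additions would be 0.5 to 2.5 points of error and the losses 1.6 to 7.8 points of power. These figures leave out the repeated-measures structure, the site term and the joint ITT/PP rule. The point deserves action because the direction is towards a false non-inferiority claim and the remedy is cheap.

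**What to change.** 1. Carry a teaching-group ID into the analysis file.
2. In 6.2.1, prespecify a random intercept for teaching group, nested in site, for the faculty-led arm (a partially nested model). Extend it to the blended arm where a stable tutor or group can be identified, and otherwise treat those students as singletons.
3. Name the cluster level of the robust standard errors: teaching group, not site. This keeps some protection when the group variance is estimated as zero.
4. In 3.3, state that the 90% power assumes no teaching-group clustering, and show power at ICC 0.05 and 0.10 (88.3% and 86.3% with the control arm only; 86.3% and 82.4% with both arms).

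No extra students and no change in trial conduct are needed. The cost is one identifier, some SAP wording, a slightly wider interval and a slightly lower stated power. The SAP shows that group size is available but not that a group ID is held for both arms, so this should be checked first.

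### The primary model includes site but no student-level baseline predictor, although previous practical ultrasound hours are collected from every student; pre-specifying them is a free, probably small, improvement

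*SAP*

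**What the plan says.** Section 6.2.1 specifies a repeated-measures linear mixed model with "fixed terms for the learning group, the type of series, the time point and the interaction term between learning group and time point". The same sentence completes the model by adding a random part, made up of "random terms for site and participant". Site is also the stratification factor: allocation is made "with allocation in a 1:1 ratio, stratified by study site" (section 3.2). Section 6.2.1 requires the ITT and PP analyses to agree before non-inferiority is established, so the lower one-sided 95% limit must exceed -1.5 points in both.

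Section 5.5 lists the prior-experience data collected at baseline: textbook ownership, "hours of previous practical experience in ultrasound, hours of formal teaching in ultrasound". Section 5.2 makes "Failure to fill out baseline questionnaire" an exclusion criterion, so these data should exist for every randomised student. Section 5.2 also excludes students with "More than 5 hours of previous formal ultrasound training". It states no corresponding limit on practical experience.

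The SAP gives the baseline variables other roles. They are summarised descriptively (section 5.5). They are considered for the imputation model if more than 5% of students have no outcome at either time point (section 6.3). Formal training also helps to define eligibility and the PP set (sections 5.2 and 4.3.2). The exploratory models are described as follows: "We will explore the association of different factors such as gender, hours of additional training, motivation for ultrasound and mean group size with OSCE scores" (section 6.2.4). Prior experience is not among the factors named there.

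**The concern.** The SAP schedules OSCEs only after the course (section 3.6), so there is no pre-course score to represent a student's starting skill. Recorded prior experience is the nearest substitute. The SAP itself treats prior formal training as relevant to the outcome, since more than 5 hours is both an exclusion and a major protocol deviation. Practical hours, the measure with no stated upper bound, are neither restricted nor adjusted for.

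Three things are at stake.

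- **Precision.** Non-inferiority depends on where a confidence limit falls relative to -1.5. A prognostic baseline covariate narrows that interval and leaves the estimated mean difference of a linear model targeting the same quantity.
- **The PP comparison.** The PP set drops students for events after randomisation: not completing the training, taking extra training, or missing an exam. Randomisation does not protect that comparison, and exclusions may differ between a self-organised 16-week course and a faculty-led one. Because PP must agree with ITT, imbalance in prior experience there bears directly on the conclusion.
- **Pre-specification.** Section 5.5 attributes baseline differences to chance but gives no rule for handling one. A covariate added after an imbalance has been seen would be a data-driven choice.

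**Working it through.** **Inputs from SAP section 3.3.** SD 4 points ("standard deviation (SD) of 4 points"), margin -1.5, assumed true difference +0.5, one-sided alpha 0.05, power 90%, 69 students per arm (138), and 152 after 9% dropout. The distance from the assumed difference to the margin is 0.5 + 1.5 = 2 points.

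**Step 1: reproduce the planned sample size without covariates.**

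n per arm = 2 × 4² × (1.645 + 1.282)² / 2² = 68.5, rounded up to 69, so 138 in total. Dropout: 138 / 0.91 = 151.6, rounded up to 152. Both stated figures reproduce. At 69 per arm, power is 90.2% by the normal approximation and 89.9% by the noncentral t. The plan therefore reaches its target power without adjustment.

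**Step 2: effect of adjustment.** Let r be the correlation between the baseline covariates and the 6-month score. The SAP does not give it, so r is an assumption and a range is shown.

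- Residual SD = 4 × √(1 − r²)
- SE of the difference = residual SD × √(2/69)
- Distance from estimate to lower limit = 1.645 × SE
- Power = Φ(D / SE − 1.645), with D = 2 at a true difference of +0.5 and D = 1.5 at a true difference of 0
- n per arm for 90% power = 68.5 × (1 − r²), rounded up

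| Assumed r | SE | Estimate to limit (points) | Power at +0.5 | Power at 0 | n per arm for 90% power at +0.5 |
|---|---|---|---|---|---|
| 0 | 0.681 | 1.120 | 90.2% | 71.2% | 69 |
| 0.1 | 0.678 | 1.115 | 90.4% | 71.5% | 68 |
| 0.2 | 0.667 | 1.098 | 91.2% | 72.7% | 66 |
| 0.3 | 0.650 | 1.069 | 92.4% | 74.7% | 63 |
| 0.4 | 0.624 | 1.027 | 94.1% | 77.6% | 58 |
| 0.5 | 0.590 | 0.970 | 96.0% | 81.6% | 52 |

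**Step 3: shift of the lower limit.** Shift = 1.120 × (1 − √(1 − r²)).

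- r = 0.1: 1.120 × 0.0050 = 0.006 points
- r = 0.3: 1.120 × 0.0461 = 0.05 points
- r = 0.5: 1.120 × 0.1340 = 0.15 points

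**Limits of the check.** This is a plain two-sample approximation. It does not represent the series term, the site and participant random terms or the robust standard errors of section 6.2.1. It ignores the small cost of the added parameters and any overlap between the covariates and site.

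**The case against.** The strongest reply is that nothing here is wrong. An analysis without optional prognostic covariates is valid under randomisation, the sample size was calculated on the unadjusted SD, and the planned power is reached. All of that stands, and it settles that this is not an error. It does not count against pre-specifying a covariate that is already collected.

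A reader might infer stronger versions of the point, and the SAP does not support them:

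- *That the model adjusts for nothing at baseline.* Site is in the model. Because recruitment is mainly from semester 7 in Bern and semester 6 in Zurich and Fribourg (section 5.3), site also carries some information on stage of study. What is missing is a student-level predictor.
- *That one confidence limit decides the trial.* ITT and PP must agree, so two limits matter.
- *That the gain is substantial.* No correlation is given. Formal teaching is restricted to 0–5 hours by eligibility, which limits what it can explain. Practical hours include watching as well as doing (section 5.5), which may be a weak proxy for skill. The rows for r = 0.4 and 0.5 only show the range; nothing in the SAP supports values that large.
- *That adjustment removes imbalance in prior skill.* It accounts only for recorded hours, under an assumed functional form.
- *That the immediate post-course OSCE could serve as the baseline.* It is measured after randomisation and is itself an outcome.

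On missing data, the joint model already uses the immediate score for students who miss only the 6-month exam, and imputation can draw on the baseline variables if its trigger is met. Any further benefit there is unquantified, and the point does not rest on it.

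**Conclusion.** The point holds as a low-cost improvement of minor weight. The primary model includes site but no student-level baseline predictor, while practical-experience hours should be available for every randomised student and have no stated cap.

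The size is uncertain and probably small. For an assumed r of 0.1 to 0.3, power at a true difference of +0.5 rises by roughly 0.3 to 2.2 percentage points. At a true difference of 0, where unadjusted power is only about 71%, it rises by roughly 0.4 to 3.5 points. These figures rest on the SAP's SD of 4, 69 evaluable students per arm, the two-sample approximation and an assumed correlation.

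The possible reduction of selection bias in the PP comparison is a separate benefit. It is partial and cannot be quantified from the SAP.

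**What to change.** In section 6.2.1, add hours of previous practical ultrasound experience as a pre-specified fixed covariate in the primary ITT and PP models. A form such as log(1 + hours) would limit the influence of a few large values; it is one reasonable choice and should be fixed before the data are seen. Hours of formal teaching may be added, with little expected from them given the 5-hour cap. State whether each covariate effect may differ by time point.

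Carry the same covariates into the separate time-point models of section 6.2.3, since these become primary if the joint model does not fit. Report the model without the covariates as a sensitivity analysis for both populations.

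The cost is SAP wording and a few degrees of freedom: with time-point interactions, two for practical hours alone and four for both covariates. No new data are needed, and the sample size need not change.
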